4.1 Data Acquisition

Data will be collected prospectively at multiple time points, including baseline/pre-ablation, intra-procedural, prior to hospital discharge, and at the 3-month follow-up post-index ablation. Patient demographic and clinical characteristics, procedural details, and concomitant medications will be recorded from medical charts. Information regarding lifestyle factors, medication adherence, adverse events, redo procedures, and quality of life (QoL) - general EQ-5D and the AF specific AFEQT assessment - will be obtained through either face-to-face interview, telephone consultations, or online platforms.

At the 1-, 2-, 3-, 6-, 9- and 12-month follow-up, arrhythmia recurrence will

be assessed using a 12-lead ECG and a 7-day Holter monitor. In this study, the Kapatch dynamic electrocardiogram monitor (Zhejiang Medical Device Registration Certificate No.: 20202070050) will be also utilized for cardiac rhythm monitoring at the 1-, 2-, 3-, 6-, 9-, and 12-month follow-up.

4.2 Procedure of Data Collection

At each site, all subjects that meet all inclusion criteria and do not have any exclusion criteria will be enrolled non-selectively.

All subjects meeting the enrollment eligibility criteria will be recorded in a patient log. Patient logs will be kept in individual participant hospitals and do not need to be submitted to the Coordinating Center. The enrolled subjects will be compared with those who meet the inclusion/exclusion criteria but are not enrolled in the study to assess the enrollment selection bias. Only subjects who have signed the informed consent are enrolled and the follow-up data including the rhythm monitoring data collected according to the study protocol. For those who are eligible but fail to enroll due to unwillingness to sign the informed consent or due to other reasons, only baseline characteristics data, procedure data and in hospital stay outcomes (severe procedure related complications, prolonged hospital stay) will be collected. An informed consent waiver is required from EC/IRB for each participating site. The data to be collected at each time point is listed in **Table 1**.

The accuracy of data collection will be validated by comparing with the source data. At least 10% of each data variable will be randomly selected for validation by EDC system. Demographical data will be 100% SDV, and the remaining data variables will be selected for validation at various ratios depending on the criticality of the variable. SDV randomization ratio will be dynamically reset by error rate of each site and each variable.

Table 1. Data collected at different time points

	Basel ine/Pr e-Ablation	Ablati on and Pre-Discharge	1M [Days 30±7]	2M [Days 60±7]	3M [Days 90±14]	6M [Days 180±30]	9M [Days 270±30]	12M [Days 365±45]
Informed Consent	√							
Face to Face interview/Tele-interview	√	√	√	√	√	√	√	√
Questionnaire	√				√	√		√
Socio-demographic	√							
Medical history	√							

Smoking, alcohol consumption	✓		✓	✓	✓	✓	✓	✓
New onset medical conditions		✓	✓	✓	✓	✓	✓	✓
Concomitant Medications	✓		(✓)	(✓)	(✓)	(✓)	(✓)	✓
Transthoracic echocardiography	(✓)	(✓)	(✓)	(✓)	(✓)	(✓)	(✓)	(✓)
Neuroimaging of the cranium	✓	✓	(✓)	(✓)	(✓)	(✓)	(✓)	(✓)
Laboratory investigations	✓	✓	✓	✓	✓	✓	✓	✓
EQ-5D	✓				✓	✓		✓
AFEQT (for AF/AFL)	✓				✓	✓		✓
Physical examination	✓	(✓)	(✓)	(✓)	(✓)	(✓)	(✓)	(✓)
Ablation Record		✓						
ECG record (Holter)	✓	✓	✓	✓	✓	✓	✓	✓
Re-ablation and ablation sites			✓	✓	✓	✓	✓	✓
SAEs		✓	✓	✓	✓	✓	✓	✓
Cardiovascular related emergency visit and hospitalization			✓	✓	✓	✓	✓	✓

4.3 Data Elements

The following data elements will be collected in three case report forms and a site questionnaire.

Pre-procedure data

The following pre-procedure data will be collected in one of the case report forms.

Demographics	age, sex, education background, medical insurance information, etc
Medical history	medical history (congestive heart failure, hypertension, coronary heart disease, diabetes, stroke/TIA history, systemic arterial embolization, bleeding history, CHADS ₂ VASC for AF, arrhythmia history) and heart surgery history
Physical examination	blood pressure, heart rate and heart rhythm, and body weight and height

Laboratory test	CBC, Electrolytes, glucose, serum cholesterol, creatinine, INR
Echocardiogram	left ventricular ejection fraction (LVEF), left atrium diameter and volume, presence and severity of mitral and tricuspid regurgitation, LAA detection methods (CT/TEE/ICE), whether there is spontaneous echo contrast in TEE examination
Concomitant Medications	blood pressure lowering drugs, diabetic medications, lipid lowering drugs, continuous or interrupted anticoagulants, AADs
Quality of life (QoL)	general EQ-5D and the AF specific AFEQT assessment

Procedural Data

The table below lists the information documented during AF ablation and pre-discharge hospital stay. These data will be collected in another case report form.

Cardiac arrhythmia	 paroxysmal AF  persistent AF <1year  Others, _____
Anesthesia or sedation level	minimal sedation, conscious sedation, deep sedation or general anesthesia
Ablation and mapping catheters	list the catheters
Procedural and ablation data	total procedure time, Mapping time and points, RF application time
Ablation strategies : Ablation sites in addition to PVI including the AI value per ablation line	Circumferential pulmonary vein isolation (CPVI) Additional: Line ablation: LA roof line/LA anterior line/LA posterior line/CTI/Mitral isthmus/SVC CFAE/Rotors/Substrate modification Others
Acute success	 Yes  No, reason: _____
VISITAG® parameters	number of tags, CF, power and energy deliver time per lesion, AI value per application and per segment, impedance drop Data will be collected in the CARTO® 3 Navigation

	
System during the ablation procedures for generation of left atrium ablation maps in accordance with predefined segments of anterior wall, ridge, posterior wall, roof and inferior area
 
VISITAG® parameters source database should be exported from Carto system and saved on One Drive. Checklist will be provided to record the participants' ID, file ID and uploading information.

ACT	Max ACT during ablation _____
Pre-discharge data	
 • Supine time after ablation • Concomitant medications (anticoagulation, AAD, BP-lowering drugs, lipid-lowering drugs, and antidiabetic drugs) • Postprocedural complications/adverse events (device/procedure-related and any SAEs) • Length of stay in hospital

Subject Follow-Up Data

Subject follow-up data are collected in the effectiveness and safety data form and include items listed in the table below:

Patient information	weight, blood pressure, QOL, EHRA score, life style,
Concomitant medications	anticoagulation, AAD, blood pressure-lowering drugs, lipid-lowering drugs, and antidiabetic drugs
Documented AF/AFL/AT recurrence	12-lead ECG/7-day Holter, AF burden in the holter
Repeat procedure	Re-ablation and ablation sites
Emergency or re-hospitalization	Cardiovascular related emergency visit and re-hospitalization due to arrhythmia recurrence or procedure-related reasons
New onset medical conditions	hypertension, diabetes, major bleeding, renal dysfunction, etc.
Serious procedure or device related adverse events	List (Appendix A)

5. Trial/Repository Administration

The trial will be conducted in compliance with this protocol, and according to ISO 14155: 2011, Clinical Investigation of Medical Devices for Human Subjects, and the International Conference on Harmonization (ICH) Harmonized Tripartite Guideline of Good Clinical Practice (E6).

5.1 Institutional Review Board/Ethics Committee

This protocol must be reviewed and approved by the appropriate IRB/EC where the trial is to be conducted before enrollment of subjects. The IRB/EC must approve in writing any changes to the protocol that affect the rights, safety, or welfare of the subjects, or may adversely affect the validity of the trial.

A signed copy of the IRB/EC Approval Form and a signed copy of the IRB/EC approval letter addressed to the investigator must be submitted to the Coordinating Center certifying registry approval before subject enrollment. Investigators are responsible for submitting and obtaining initial and continuing review of the trial by their IRB/EC.

5.2 Responsibilities

The investigator is responsible for ensuring the trial is conducted in accordance with the procedures and evaluations described in this protocol (see Investigator Signature Page at the beginning of this protocol).

Deviations from the protocol shall not be made without discussion with the Coordinating Center. Changes to the protocol may be made only when a written protocol amendment provided by the sponsor has been signed by the investigator and approved by the IRB/EC and applicable regulatory agencies in accordance with local requirements.

5.3 Restrictions

Only staff listed in the delegation can log in the internet-based data management system with an authorized account and the unique individual password.

5.4 Confidentiality

Authentication technology is adopted to meet demands like identity authentication and non-repudiation. Sensitive data will be stored via a data encryption technology and cross-domain data transfer will be encrypted. The present trial will sign a confidentiality agreement with the staff who manage and operate the important information. Information manager should not modify or delete the existing information without authorization. Unrelated people are restricted to access to the clinical research EDC system.

Data managers will daily check all the uploaded data case by case, and if there's a question, he/she shall raise it and send a reminder to the investigator. Data managers are served by experienced physicians from HHRC. All questions will be listed with the content, questioner, proposed date and resolved date recorded in detail.

The study team will retain all study records required by the HHRC and by the applicable regulatory bodies in a secure and safe facility for a minimum period of 15 years.

The Sir Run Run Shaw Hospital Clinical Trials Centre will function as the

coordinating centre for all aspects of this trial. The Data Management Coordinating Centre will oversee the intra-study data sharing process, with input from the Data Management Subcommittee.

All Principal Investigators will be given access to the cleaned data sets. Project data sets will be housed on the Project Web Database and/or the file transfer protocol site created for the study, and all data sets will be password protected. Project Principal Investigators will have direct access to their own site's data sets and will have access to other sites data by request. To ensure confidentiality, data dispersed to project team members will be blinded of any identifying participant information.

5.5 Private Health Information (PHI)

Subjects will be identified on the case report form by number codes only, using the criteria provided by the coordinating center. Local IRB approval is required for each participating site.

All information and data sent to the Coordinating Center concerning subjects or their participation in this trial will be considered confidential. Only authorized Coordinating Center personnel or designee, or local government authorities acting in their official capacities will have access to these confidential files. All data used in the analysis and reporting of this evaluation will be without identifiable reference to the subject.

6. Data Collection and Management

The Coordinating Center will perform all data management activities for this trial. These activities include development and validation of a clinical database into which all trial data will be entered. The Coordinating Center will be responsible for ensuring overall integrity of the data and database. Data will be stored on a secure cloud server. Only authorized study person will be able to access EDC. ID and password will be used to protect data security.

6.1 Data Collection

Case Report Forms (CRF) will be used to collect all subject data for the trial. The CRF will be developed to capture the information outlined in this protocol. Data collected on these CRFs will be entered to an Electronic Data Capture (EDC) System by individuals at the Coordinating Center and analyzed by the trial Sponsor as defined in the trial protocol.

6.2 Data Reporting

The site investigator, or a designated individual, is responsible for ensuring that trial data are properly recorded on each subject's CRF and related documents. Completed CRFs will be reviewed by Coordinating Center personnel throughout the trial.

All CRFs should be completed and submitted to the Coordinating Center using the guidelines set for by the Coordinating Center. For AE reporting,

refer to the Adverse Event Reporting Requirements and timelines within this trial protocol.

6.3 Source Documentation

Source documents will serve as the basis for validation of data entered into the EDC system. Source documents may include subject medical records, hospital charts, clinical charts, the investigator's subject registry files, admissions and discharge summaries, as well as the results of diagnostic tests such as X-rays, laboratory tests, and electrocardiograms.

If no standard hospital or office document exists to capture information that may be unique to this trial, a worksheet may be developed to record this information, which shall be signed by the PI at the given site and serve as the source document for unique trial data.

Electronic subject records will be considered source documents on the condition that the hospital's database is a validated system. If this is not the case, electronic records will have to be printed and added to the subject's paper file.

Regulations require that investigators maintain information in the subject's medical records, which corroborate data collected on the CRF.

Variables collected will be validated with source data. Demographical data will be 100% SDV, and the rest of data to be set up different randomization ratio, based on the variable priority. At least 10% of transferred data will be randomly selected by EDC system.

If there are no discrepancies, then monitor does not have to SDV anymore data for that visit. If there are discrepancies, then the amount to SDV will increase by 10% and will continue to increase until 50%. If discrepancies are still found after 50%, then all data will have to be SDV. The Site Monitor may also check the compliance of the site with the protocol and to detect issues that may be difficult to assess from remote monitoring alone.

The Project Manager – he/she will be responsible for the day to day running of the study including liaising with the individual study sites and study research co-coordinators. This individual will supervise the activities of the Study Nurses with respect to patient eligibility, data accumulation and transmission, and patient follow-up.

There will also be a separate and independent data safety and monitoring board (DSMB). The DSMB will consist of three people. All members of the DSMB have extensive clinical trials experience and were invited on the basis of their expertise and independence. The DSMB will monitor the study safety data on an ongoing basis.

6.4 Missing Data Handling

This study is a real-world study, and all the data will be recorded based on the medical routine of the hospital and the actual completed status of the subjects. If there are missing data, compliance with medical routine is not

considered as a protocol deviation.

6.5 Energy Composition Target and Monitoring

Each participating center is required to maintain complete documentation of the ablation energy modality selected for all enrolled cases. Following the effective date of this protocol version, the Coordinating Center will periodically review and summarize the energy composition of newly enrolled patients to assess whether the overall distribution aligns with the anticipated study trajectory.

To ensure that the study cohort adequately reflects the increasing clinical adoption of PFA and maintains relevance in a future PFA-dominant treatment environment, the study establishes the following population-level target for the overall energy composition during the study period:

Across the entire enrollment period, the cumulative proportion of PFA cases is expected, in principle, to reach at least 50-60% of all enrolled subjects.

This target is intended to optimize the cohort's energy structure at the population level and enhance the interpretability and external validity of study results in the context of evolving ablation practice. It does **not** impose restrictions on the energy selection for individual cases and does **not** constitute a mandatory requirement for any participating center or investigator. This monitoring process is implemented solely to support study quality control and consistency in data interpretation.

7. Adverse Event Evaluation, Record and Report

7.1 Adverse event

Adverse events (AE) mean any untoward medical occurrence during clinical trials, whether related to catheter ablation. An AE can be any adverse or unexpected sign associated with catheter ablation in time, a symptom reported by a subject, or any disease, whether or not it has a causal relationship with catheter ablation.

7.2 Serious adverse events

Serious adverse event (SAE) refers to an event or reaction that, in the view of either the investigator or sponsor, results in any of the following outcomes: death, a life-threatening adverse event, in-patient hospitalization or prolongation of existing hospitalization, a persistent or significant incapacity or substantial disruption of the ability to conduct normal life functions, or a congenital anomaly or birth defect.

7.3 Suspected Unexpected Serious Adverse Reactions (SUSARs)

SUSARs refer an adverse event that occurs in a clinical trial subject, which is assessed by the sponsor and or study investigator as being unexpected, serious and as having a reasonable possibility of a causal relationship with the ablation.

An independent Advisory Committee comprising clinical electrophysiologists, device experts, and procedural workflow specialists will provide non-binding recommendations throughout the course of the trial. This committee will offer guidance on clinical protocol development, training procedures, data interpretation, and integration of new technologies as they become available. The Advisory Committee does not have access to unblinded safety data but will work in coordination with the Sponsor and DSMB to ensure the trial remains aligned with current clinical practice standards and technological advancements.

7.4 Device defects

Device defects refer to unreasonable risks that may likely cause or contribute to a death or serious injury under common practice, such as label errors, quality problems, malfunction, etc.

7.5 Collect and report serious adverse events, device defects, and unexpected serious adverse events

7.5.1 Collection time

AE evaluation will be conducted from the signing of informed consent to the end of this trial.

7.5.2 SAE Reporting

After initial receipt of SAEs, the investigator should provide proper treatment and write to the relative facilities and sponsor immediately.

The investigator is responsible for continuing to follow all SAE reports (whether related to study drug) until resolution or until the event is considered chronic and/or stable by the investigator and/or other physician who has the responsibility for the patient's medical care. Follow-up SAE reports will be reported according to the same timelines as initial reports as soon as new significant information becomes available.

For SAE or suspected SAE-related device defects, the sponsor should report to the CFDA and the health authority at the same level and notice other sites in this trial. Study sites should report to the ethnic committee by the clinical trial management department.

7.5.3 Device defects Reporting

If any issues with the study device arise, including suspected or confirmed malfunctions related to quality, labeling, durability, reliability, or safety, please contact the designated Johnson & Johnson representative immediately.

7.5.4 SUSARs Reporting

Suspected Unexpected Serious Adverse Reactions [SUSARs] will undergo expedited reporting to relevant regulatory authorities (e.g., research ethics committees, National Medical Products Administration, and National Health

Commission of the People's Republic of China). Investigators must report all SUSARs to sponsor as soon as possible and 24h of learning of the event. These SUSARs will be centrally reviewed and reported by the sponsor as soon as possible:

For fatal or life-threatening SUSARs, sponsor must report as soon as possible and within 7 days of learning of the events. Active follow-up must be completed within the following 8 days (The first day of learning of the event is considered 0 day).

For fatal or life-threatening SUSARs, sponsor must report as soon as possible and within 15 days of learning of the events.

8. Statistical analysis

Continuous variables are expressed as mean \pm SD if normally distributed or median (interquartile range [IQR]) if not normally distributed. Intergroup differences will be compared by student's t-test (normally distributed data with equal variance) or Mann-Whitney U test (failed either normality or equal variance test). Categorical variables will be presented as percentages and compared by using the Chi-square test or Fisher's exact test. The Kaplan-Meier method will be used to describe event-free rates over time. The statistical significance for all tests will be accepted at $P < 0.05$.

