3.4.2 Secondary endpoints

[figure not shown]
- The acute success of the procedure.
- The proportion of intraoperative conversion to using X-ray.
- Utilization of lead personal protective equipment (PPE) and wear time.Well-being survey of staff.
- The proportion of patients with recurrence of targeted arrhythmia during the first 90 days post-ablation.
- Early recurrence of atrial arrhythmias, defined as any AF/AFL/AT episode lasting >30 seconds occurring during the blanking period.
- Late recurrence of atrial arrhythmias, defined as any documented AF/AFL/AT episode lasting >30 seconds occurring after the blanking period and up to 12 months.
- Impact of early recurrence on late recurrence, assessed through survival analysis and multivariable adjustment to evaluate whether early recurrence predicts subsequent late recurrence.
- AF burden, assessed by scheduled rhythm monitoring (e.g., 7-day Holter at 3, 6, 9, and 12 months), expressed as the proportion of time spent in AF during the monitoring period.
- Incidence of peri-procedural complication.
- Total procedure duration, ablation time.
- changes in quality-of-life (using the AF Effect on Quality of Life (AFQT) and the EuroQol Health-Related Quality-of-Life 3-Level (EQ-5D-3L)).

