3.5 Sample Size

For **efficacy** as the primary endpoint, sample-size was calculated by non-inferiority log-rank test with 1:1 design. The expected recurrence rate of AF is 30% for control group based on previous studies and our experience, and a hazard ratio of 1.3 was used for establish non-inferiority. Based on a power of 80% and an alpha of 0.05, proportion lost to follow up 5%, a sample size of **724 patients (362 for each group)** was estimated.

Safety endpoints will still be collected in detail and analyzed for comparison between the groups, but they will not be used to determine the sample size.

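### Section 8 provides only unadjusted tests for change in quality of life; adjusting for the scheduled baseline score would give a more precise comparison at no cost (low severity)

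*Protocol*

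**What the plan says.** Section 8 describes how continuous variables are summarised and compared. Between groups it uses Student's "t-test (normally distributed data with equal variance) or Mann-Whitney U test (failed either normality or equal variance test". "The statistical significance for all tests will be accepted at" P < 0.05. The paragraph is general and does not name quality of life.

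Section 3.4.2 lists as a secondary endpoint "changes in quality-of-life (using the AF Effect on Quality of Life (AFQT" and EQ-5D; the synopsis lists it too. Table 1 in Section 4.2 has a row for "AFEQT (for AF/AFL" and one for EQ-5D, both ticked without brackets at baseline, 3, 6 and 12 months. Section 4.3 includes "general EQ-5D and the AF specific AFEQT assessment" among the pre-procedure data.

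The only covariate adjustment mentioned in the protocol is in Section 3.4.2. It concerns whether early recurrence predicts late recurrence, not quality of life.

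**The concern.** Quality of life is measured before treatment with the same instruments used afterwards, and a patient's baseline score is often one of the best predictors of the later score. The stated tests do not use it as a covariate.

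- **Precision.** A change score gives the baseline a fixed weight of one. Unless that happens to be the true regression slope, noise is left in the comparison that a covariate would remove.
- **Chance imbalance.** With equal SDs and ρ below 1, a chance baseline difference between arms carries into the change score with weight (1−ρ) and opposite sign. Over repeated randomisations this averages to zero, but in the one trial that is run it does not.
- **Method chosen by the data.** A normality or variance pre-test decides between a comparison of means and a rank test, and could decide differently for AFEQT and EQ-5D. For the rank branch, Section 8 describes medians and a P value, not an estimated difference with an interval.

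At stake is the width of the interval on a patient-reported secondary endpoint.

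**Working it through.** **The plan's own figure.** The protocol gives no SD, correlation, target difference or power for quality of life. Its sample size, "724 patients (362 for each group", belongs to the primary efficacy endpoint ("Based on a power of 80% and an alpha of 0.05, proportion lost to follow up 5"%). It reproduces from the software row in the synopsis: a one-sided 0.05 log-rank test at hazard ratio 1.3 needs 360 events. With hazard 0.30 per year, loss 0.05 per year, 1 year of accrual and 3 years in total, the event probability is 0.498. That gives N = 721.4, and power 0.801 at 724 against the printed 0.8003 at 723. Whether a 3-year total fits 12-month follow-up is a separate question. No quality-of-life quantity enters this calculation.

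**Inputs.**
- 724 patients, 1:1, 5% loss (Section 3.5): 724 × 0.95 ≈ 688 evaluable, 344 per arm. Applying this loss to quality of life is an assumption.
- Baseline-to-follow-up correlation ρ: not in the protocol; assumed 0.3 to 0.7.
- Ratio k of follow-up SD to baseline SD: not in the protocol; 1, then 0.7 to 1.3.
- Two-sided 0.05 (Section 8 does not state sides) and, for power only, an assumed arm difference of 0.2 SD.

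**Formulas.** In units of the baseline variance, the per-patient variance behind the arm difference is:
- change score: 1 + k² − 2ρk, which is 2(1−ρ) when k = 1;
- baseline-adjusted: k²(1−ρ²), which is 1−ρ² when k = 1.

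The first minus the second is (1−ρk)², which is never negative. Adjustment therefore cannot be less precise, apart from one degree of freedom. When k = 1, the ratio of adjusted to change-score variance is (1−ρ²) / [2(1−ρ)] = (1+ρ)/2.

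**Equal SDs (k = 1).**

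| ρ | Change score | Adjusted | Ratio | SE smaller by | 688 patients by change score are worth | Power at 0.2 SD, change score | Power at 0.2 SD, adjusted |
|---|---|---|---|---|---|---|---|
| 0.3 | 1.40 | 0.91 | 0.65 | 19% | 447 adjusted | 60% | 79% |
| 0.5 | 1.00 | 0.75 | 0.75 | 13% | 516 adjusted | 75% | 86% |
| 0.7 | 0.60 | 0.51 | 0.85 | 8% | 585 adjusted | 92% | 96% |

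The third-last column is 688 × ratio, for example 688 × 0.65 ≈ 447. Simulating 3,000 trials of 344 per arm gave ratios of 0.65, 0.74 and 0.86.

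**Unequal SDs.**

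| ρ | k = 0.7 | k = 1.3 |
|---|---|---|
| 0.3 | 0.42 | 0.81 |
| 0.5 | 0.47 | 0.91 |
| 0.7 | 0.49 | 0.99 |

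For example, k = 0.7 and ρ = 0.3 give 0.49 × 0.91 / (1 + 0.49 − 0.42) = 0.446 / 1.07 = 0.42. At the other end, k = 1.3 and ρ = 0.7 give 1.69 × 0.51 / (1 + 1.69 − 1.82) = 0.862 / 0.87 = 0.99, because ρk = 0.91 is close to one.

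**The case against.** The strongest reply is that Section 8 is a generic paragraph and that the model for a repeated patient-reported outcome commonly sits in an SAP, which was not available here. It is true that applying the rule to quality of life is an inference. But Section 8 does fix a method for continuous between-group differences, and the protocol offers no other. If an SAP specifies an adjusted model, the two documents need aligning.

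The second reply concerns size. The gain rests on a correlation and SDs that the protocol does not give. With a larger follow-up SD and a high correlation it almost vanishes. That stands, and is why a range is shown.

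A reader might also infer more than the documents support:
- **That baseline is ignored.** The endpoint is change, so each patient's baseline is subtracted; the loss is partial.
- **That the visits are tested one by one.** Table 1 gives collection times only; no section says how the visits enter the analysis.
- **That the trial sets out to show preserved quality of life.** The hypotheses in Sections 1.2.1 and 3.2 are non-inferior efficacy and safety. The research questions in Section 1.2.2 do not include quality of life, and no margin is set for it.
- **That every patient will have a baseline score.** It is scheduled, but Section 6.4 says "all the data will be recorded based on the medical routine of the hospital" and tolerates gaps.

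**Conclusion.** The point holds as a matter of efficiency, at low severity. Read as the only rule available, Section 8 gives change in quality of life an unbiased but less precise comparison than the scheduled data allow. With equal SDs and ρ from 0.7 down to 0.3, it gives up 15% to 35% of the information. Allowing the follow-up SD to be 0.7 to 1.3 times the baseline SD widens this to between about 1% and 58%. These figures assume 1:1 allocation, the same linear relation of follow-up to baseline in both arms, and baseline scores that are in fact collected.

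It would be wrong to infer a biased result or a threat to the trial's main conclusion. Randomisation protects the unadjusted comparison, the endpoint is secondary and unpowered, and the primary endpoints and N = 724 do not depend on it.

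The case is firmer for AFEQT than for EQ-5D. Section 3.4.2 names the 3-level EQ-5D while Appendix C prints a 5-level form. That form asks about health averaged over the time since study entry, which does not fit a baseline visit.

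**What to change.** Add to Section 8 that AFEQT and EQ-5D scores will be compared between arms by a linear model with the baseline score as covariate: either ANCOVA, or a mixed model over the 3-, 6- and 12-month visits. Report the adjusted mean difference with its 95% CI. State that no normality or variance pre-test chooses the method for these outcomes; Mann-Whitney may stay as a sensitivity analysis.

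Before the EQ-5D baseline is used as a covariate, reconcile Section 3.4.2 with Appendix C on the version, and settle what period the baseline form refers to.

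The analysis change costs one or two sentences, with no new visits, data or patients. It should be made before outcome data are analysed, so that the adjustment cannot look data-driven. The EQ-5D reconciliation is a document correction that is needed in any case.
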